**Research Participants Who Are Not Yet Adults (infants, children, teenagers)**

I am not enrolling participants who are not yet adults in this research study. – *please leave the rest of this section blank*

1. Will parental permission be obtained from:

Page 10 of 29

One parent even if the other parent is alive, known, competent, reasonably available, and shares legal responsibility for the care and custody of the child

Both parents unless one parent is deceased, unknown, incompetent, or not reasonably available, or when only one parent has legal responsibility for the care and custody of the child

Requesting a waiver of parental permission

**If you are getting parental/guardian permission:**

1. Indicate how you will be documenting the permission:

Signed consent form

Requesting a waiver of documentation of parental permission

2. Describe whether permission will be obtained from individuals other than parents, and if so, who will be allowed to provide permission. Describe the process used to determine these individuals' authority to consent to each child's participation in research.

**If a waiver of parental permission is being requested:**

1. Describe how the study is designed for a subject population for which parental/guardian permission is not a reasonable requirement to protect the subjects, if applicable.

2. Describe how the research could not practicably be carried out without the waiver of parental permission.

a. Indicate if the subjects will be provided with additional information about the study after participation.

3. Will assent be obtained from:

all of the children

some of the children

none of the children

If assent will be obtained from some children, indicate which children will be required to assent.

When assent of children is obtained, describe how it will be documented.

4. For children who are pregnant, describe how assent and permission are obtained.

N/A

**Sharing of Results with Research Participants**

Results will be shared with research participants:

Yes  No

Page 11 of 29

If yes, describe how the results will be shared.

*Study participants will receive a one-page summary of the results by mail or email based on contact preference.*

Results will be shared with others:

Yes  No

If yes, describe with whom and how the results will be shared.

*Results of the study will be shared with others through manuscripts and presentations.*

## **Study Design/Procedures**

**Directions: 1) Describe the overall study design. 2) Provide a description of all study-related research procedures being performed, including the length of time involved. 3) Include procedures being performed to monitor research participants for safety or minimize risks. 4) Describe the source records including medical or educational records, which will be used to collect data about subjects.**

*The study is a four-year randomized controlled trial in Northeastern Ohio and includes a convenience sample of family caregivers of adults with bipolar disorder. After eligibility is verified during phone screening by team member, the consent forms will be reviewed verbally, questions about the study will be answered, and the study enrollment/first data collection appointment will be made.*

*There are three structured data collection time points (T1/enrollment, T2/ 6months after initiation of intervention, T3/ 12 months after initiation of intervention); these will be face-to-face with a research assistant, using a desktop, laptop, or iPad with secure REDCap software. During the enrollment and first data collection meeting, we will obtain informed consent from the caregiver. Caregivers will have time to ask questions about the study and review the consent form before signing it.*

**COVID-19 Modifications:** Some T2 and T3 data collection will take place remotely, as a response to the COVID-19 pandemic (beginning in April 2020). We will use phone (Google voice) or Zoom (computer video) to complete the data collection. An email will be sent, if possible, to participants with the answer response choices for each survey. If we are using phone for data collection, the Research Assistant (RA) will ask the participant each question and record the responses in our REDCap Surveys project. If collecting data using Zoom video, the RA will share the screen of the REDCap Surveys project, and record the answers for the participant as they review each survey question. If neither of those two options are available for the participant (e.g., limited phone minutes, inability to use Zoom), the study may email the REDCap surveys to study participants for them to complete on their own at an agreed upon date / time (similar to in-person appointment); in this instance, the RA can be available to answer questions or clarify information as needed, by phone or email. It may be that none of these options will work for a study participant, in which case we will consider that data "missed" if we cannot wait to collect the data in person at a later date (when we resume normal study activities). The precise method(s) will depend on the ability and resources of the study participant. For these data collection sessions, HRV data (collected by placing electrodes on the wrists) may not be collected and will be considered missing data (see following page for more detail regarding remote HRV data collection). We will contact active participants with Zoom/ phone instructions, by phone/text and/or email, as needed, and we will record the methods used

for each data collection done remotely. A COVID-19 questionnaire will be asked at remaining T2 and T3 data collections; script to obtain consent for these questions is included in the questionnaire.

Individuals will be assigned a study ID using our enrollment log. In addition, at enrollment we will collect demographic information including age, gender, race, ethnicity, marital status, education, income, occupation, hours of work/week, if the participant is an employee or student at CWRU, health conditions, current medications, relation to person with bipolar, age of family member with bipolar, how many years ago was family member diagnosed with bipolar disorder, specific diagnosis of family member, predominant behavior style of family member with bipolar, whether or not caregiver lives with this family member, whether or not caregiver provides care/assists with basic needs (and how many hrs/day), how many years caregiver has been providing care, if other adults help provide care for family member with bipolar disorder. Some, but not all of the demographic and other questions asked at baseline will also be asked at T2 and T3. We will then proceed with data collection, consisting of surveys to measure bipolar symptoms, caregiver reactions, caregiving involvement, bipolar knowledge, resourcefulness, health risks, and health outcomes. They will also have their heart rate variability (HRV) measured using a non-invasive device on the wrists; it

will take approximately 10 minutes to collect the data. The entire first meeting will take approximately 60-90 minutes. The second and third data collection meeting will be approximately 60 minutes. In the event there is an equipment malfunction or a poor reading is obtained by a research team member, we may need to re-collect the HRV and/or survey data again after a data collection meeting. **COVID-19 modification:** HRV data will not be collected when data collection is done remotely (T2 or T3 only) and will be considered missing data. When we are able to collect HRV data, we will do so by bringing an HRV device to the study participant at a set date and time, providing instructions on how to use the HRV device, safety information on the HRV device, and also providing support via phone or video. HRV data collected this way will be collected for 15-20 minutes instead of 10 minutes, to ensure reliable data is collected. A study team member will collect the HRV device the same day or within 28 hours, at a mutually convenient time. Each HRV device will be sanitized before and after each study participants' use.

Following the T1 data collection, the project manager will randomize each caregiver into one of four groups using Qminim, a secure online minimization program. Research assistants will be blinded as to which intervention arm caregivers are assigned to. The four groups are: 1) control group- no intervention; 2) usual care group- will receive bipolar education; 3) Self-management (SM)- need based, determined by baseline cut scores from T1- either bipolar education (ED), biofeedback (BF), resourcefulness training (RT), or no need; 4) SM-preference-based, caregiver selects intervention (ED, BF, RT, or no intervention). For SM-need, for example, caregivers scoring <70% on bipolar knowledge would be assigned to ED, < 97 on the resourcefulness scale to RT, and low HRV as determined by SDNN parameter for age and gender to BF. Those in the SM-need and SM-preference groups will perform one SM intervention (as listed above). Those in the usual care group will receive the same bipolar educational intervention as others in the SM-need or SM-preference groups. All interventions will take 4 weeks and these 4 weeks will occur between the T1 and T2 data collections; the T2 data collection is planned to occur 6 months after the initiation of the intervention. The T3 data

we are excluding pregnant women from joining the study (due to the variance in HRV data which would affect scoring for minimization), if someone becomes pregnant while they are enrolled in the study, we will not exclude them from the remainder of the study.

Caregivers in the control group will receive a phone call (or email/text depending on their preferred method of contact) letting them know of their assignment; they will also have access to three interventions at the end of the study. Caregivers in the usual care, SM-need and SM-preference groups will receive training by a trained interventionist, which consists of a single face-to-face session in the caregiver's home/private venue. The session includes training/education via a voice-over PowerPoint presentation on iPad or laptop, and print materials to keep/review regarding the intervention. Other commonalities during the single session for ED, RT and BF are: 1) all caregivers will keep a structured journal, though the content will differ by intervention; journals will be collected after 4 weeks/ 28 days; 2) all will be taught to indicate day and time of the journal entry with the suggestion to do it at the same time each day; and 3) all will have the opportunity to complete a journal entry during the training session. During the 28-days after the initial session, all caregivers will: 1) perform the assigned intervention independently; 2) have print access to intervention content for review as they wish; 3) receive weekly follow-up from interventionists (3-5 minute phone call or email).

The ED and RT interventions involve providing educational information about bipolar disorder or teaching self-help (stress management, problem-solving) and help-seeking skills, respectively. BF training consists of the use of a hand-held device that shows the participant their changes in heart rate based on changes in their breathing patterns (as they relax); caregivers who need or prefer the biofeedback will be given a device to use for the study (for 28 days). Caregivers may use their intervention whenever and as often as they wish (i.e. self-tailoring). Dosing (number of times intervention is performed) and fidelity (using checklists) will be monitored. After 28 days, we will collect the BF hand-held devices and journals from all three interventions.

*Individuals will be encouraged to continue with the interventions if they found them helpful (for BF, caregivers will have been given information on deep-breathing techniques without using a device). Caregivers who cannot be reached by phone or email for follow-up (either intervention or data collection) will have a letter sent to them if they have consented to having a letter sent to their home. Occasionally, calls will need to be made to study participants outside of the office (e.g., evenings/ weekends; when a research team member is working remotely/ in the field) or participants will request to be contacted by text. In these instances, the research team will use Google Voice, which allows users (research team) to set up a phone number through their CWRU email and is connected to their personal mobile phones. Calls and texts can be made to/ from the mobile phones while masking the actual phone number. When the research team is not working, calls will be directed to voicemail.*

*From Modification #8 (approved 03/06/2019)-- At the end of the T3 data collection, study participants will receive a brochure from each of the three interventions being researched, as well as an answer sheet for Caregiver Knowledge of Bipolar Disorder Questionnaire. Study participants who received an intervention will be asked a series of questions (up to 16) about their experience with, and opinion of, the intervention they received. Study participants who have already completed all three data collection sessions and have already agreed to be contacted for any questionnaire follow-up will be called and asked questions over the phone.*

Page 14 of 29

*The supplemental analysis will use baseline data (T1) to explore relationships among caregiver characteristics (race and gender), psychological stress (caregiver reactions and caregiving involvement), and physiological stress (heart rate variability time and frequency domains). De-identified baseline data from the demographic measures, psychosocial measures (caregiver reactions, caregiver involvement) and the HRV measurements will be used for this analysis.*

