*When a person contacts the study to be screened, they will receive a screening ID in the screening log. Contact information will then be collected including name, telephone number(s) and/or email address(es) on all individuals screened will be collected for our screening log; this information will be stored in a password-protected computer file.*

*The project manager or other trained research staff will screen by phone to ensure that caregivers are at least 18 years old, have a family member with bipolar disorder who is at least 18 years old, and have cared/supported them for at least 6 months, but not necessarily in the same household, live in the study area, and have the physical capability to perform the interventions (i.e. does not have a pacemaker, is not currently pregnant). We will also be collecting demographic information (gender, race, ethnicity). All screening documentation will be kept in a screening for on REDCap.*

*We will also ask study participants if they would like to be contacted for future research; we let them know there is no penalty to them if they do not wish to be contacted. Furthermore, we inform them that agreeing to be contacted does not obligate them to participate in future research, this only permits us to contact them. We will maintain a password-protected list on Box.com of individuals that have consented to be contacted for future research, along with their contact information and contact preferences. This list will be maintained by the Project Manager and may be shared with research team case-by-case basis.*

Page 6 of 29

*After eligibility is verified during phone screening by team member, the consent form will be reviewed verbally, questions about the study will be answered, and the study enrollment/first data collection appointment will be made.*

5. Describe the feasibility of recruiting the required number of suitable research participants within the agreed recruitment period. For example, how many potential research participants do you have access to?

*Based on previous research by the PI and Co-Is, we conservatively estimate that 1 in 5 caregivers may not meet eligibility criteria. Thus, we will screen 450 potential participants to obtain the desired sample size of 360.*

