## **Data Analysis Plan**

**Directions: Describe the data analysis plan, including any statistical procedures. If applicable, provide a power analysis, and study/safety endpoints.**

*The primary aim (A1) is to examine differences across four groups of family caregivers on caregiver health over time. The underlying analyses for A1 are built around the repeated measures analysis of variance (RMANOVA). The primary analysis will be a set of 4 group X 3 time waves RMANOVA. These analyses will compare the four groups: 1) a control group (no intervention); 2) education (usual care); 3) SM-need; or 4) SM-preference across three time waves of health risks and physical and mental health outcomes. When using RMANOVA, one not only assesses mean differences across time, but also assesses group differences and the interaction of time X group, which allow us to test the trend of the means over time across the four groups.*

*The RMANOVA, not only can be used to determine if there are mean differences across the three time periods, it can utilize orthogonal polynomial contrasts to determine if there are mean and quadratic trends of the means across time. Orthogonal polynomials are weights assigned to each time period that model a linear or quadratic non-linear trend. RMANOVA can determine if these trends in the mean are significant. A linear trend is indicated if there is a change in direction based on scores across the time waves. The major assumption to be tested with RMANOVA is sphericity. Sphericity is a form of compound symmetry and refers to the equality of variances of the differences between time waves. If the assumption of sphericity is violated based on the Mauchly's test, SPSS provides and adjusted F, df, and P-value in RMANOVA to account for the violation.*

*Secondary aims are to: A2) explore whether caregiver need or their preference for interventions associated with: a) care recipient's symptoms; b) caregiver reactions; and c)*

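### Caregivers are allocated by minimisation with HRV in the scoring, but the A1 model holds only group and time, so the between-subject group test is conservative if those factors predict the outcome

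*Combined protocol and SAP*

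**What the plan says.** Study Design/Procedures states that, once T1 data are in, "the project manager will randomize each caregiver into one of four groups using Qminim, a secure online minimization program". The only factor that can be identified is HRV. Its role appears in a parenthesis explaining why pregnant women are not enrolled: "due to the variance in HRV data which would affect scoring for minimization". The other factors, their cut-points and weights, and the random element are not listed.

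The Data Analysis Plan says of A1: "The primary analysis will be a set of 4 group X 3 time waves RMANOVA". It adds that the method "also assesses group differences and the interaction of time X group", so the group effect and the interaction are both tested. No covariate is named there, and no other section adds one.

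The waves are T1 at enrolment, then 6 and 12 months after the start of the intervention ("There are three structured data collection time points"). The target is given under Recruitment Methods ("obtain the desired sample size of 360"). The template for the analysis section asks for a power analysis ("If applicable, provide a power analysis, and study/safety endpoints"), but none is given. No significance level, effect size, SD, ICC or allocation ratio is stated.

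**The concern.** Minimisation makes the arms alike on its factors, so arm means differ less by chance than under simple randomisation. An ANOVA without the factors estimates error as if allocation had been simple: variation between caregivers due to the factors stays in the between-subject error, although the design has largely removed it from the arm comparison. The F ratio for group is then too small on average. The test rejects a true null less often than its nominal level and misses real differences more often than it need.

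This is a separate matter from adjusting for the T1 value of the outcome. The minimisation factors are different variables, and they define how caregivers were allocated. A1 is the primary aim, so precision that the design has already paid for would go unused in one of its tests.

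**Working it through.** The plan has no power figure to reproduce. What follows is a range under stated assumptions.

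**Inputs from the documents:** N = 360; 4 groups; 3 waves, with T1 before allocation; model terms group, time and group by time.

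**Assumed:** equal allocation (90 per group); alpha 0.05; SD 1 at each wave; no dropout; ICC 0.5 (0.7 as sensitivity); a gain of 0.35 SD at T2 and T3 in the two self-management arms and none in the other two; three binary factors with stable effects explaining a share R2 of single-wave variance.

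**Step 1. Variance of a caregiver's mean over the three waves.** V = ICC + (1 − ICC)/3 = 0.5 + 0.5/3 = 0.667. With the factors in the model it is V − R2.

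**Step 2. Signal.** T1 cannot respond to treatment, so the shift in the three-wave mean is 0.35 × 2/3 = 0.233. Each arm mean lies 0.117 from the grand mean. The noncentrality is λ = 90 × 4 × 0.1167² / variance = 4.9 / variance.

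**Step 3. Power of the group effect** (noncentral F; 3 and 356 df without the factors, 3 and 353 with them).

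| R2 | Error inflation V/(V − R2) | λ with factors | Power with factors |
|---|---|---|---|
| 0 | 1.00 | 7.35 | 0.608 |
| 0.05 | 1.08 | 7.95 | 0.645 |
| 0.10 | 1.18 | 8.65 | 0.687 |
| 0.20 | 1.43 | 10.50 | 0.778 |
| 0.30 | 1.82 | 13.36 | 0.877 |

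Without the factors, λ = 4.9/0.667 = 7.35 and power is about 0.61. With ICC 0.7, V = 0.8 and λ = 6.125: power is 0.52 without the factors and 0.55, 0.58, 0.66 and 0.75 with them at R2 of 0.05, 0.10, 0.20 and 0.30.

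**Step 4. Simulation of the allocation itself.** Minimisation on three binary factors, 90% to the minimising arm, ICC 0.5, 2,500 runs per setting, and an effect of 0.4 SD (not 0.35) for power. The Monte Carlo standard error at 5% is √(0.05 × 0.95/2500) = 0.004.

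| R2 | Size of nominal 5% group test, without / with factors | Power at 0.4 SD, without / with factors |
|---|---|---|
| 0.05 | 0.032 / 0.044 | 0.737 / 0.773 |
| 0.10 | 0.028 / 0.055 | 0.752 / 0.832 |
| 0.20 | 0.011 / 0.060 | 0.748 / 0.888 |
| 0.30 | 0.004 / 0.056 | 0.756 / 0.955 |

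**Step 5. Group by time, same simulation.** With stable factor effects nothing is lost: size 0.043 to 0.054 and power 0.92 to 0.94 with or without the factors. If the factors act only at T2 and T3 (R2 0.20 there, ICC 0.6), the unadjusted interaction test is conservative too: size 0.020 against 0.045, power 0.948 against 0.975.

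**The case against.** The strongest reply is that A1 asks about differences over time, and group by time is the term that carries this. T1 precedes allocation, so the group main effect averages in a wave that treatment cannot move, while stable differences between caregivers cancel from the interaction. Under the assumptions above, at 0.35 SD, the interaction has λ = 90 × 4 × 0.175² × (2/3)/(1 − ICC) = 14.7 and power of about 0.83 at ICC 0.5 (6 and 712 df), against 0.61 for the group effect. This stands, and it confines the point. It does not remove it, because the plan tests group differences as well.

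It is also fair that the size cannot be known. HRV is identified only in passing, the remaining factors are unlisted, and if none predicts the outcome the loss is nil. This stands too.

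Four stronger readings are tempting and are not supported:
- That a stated 5% level is breached. No alpha appears anywhere in the documents; 5% is a convention adopted here.
- That A1 as a whole loses power. The interaction does so only if a factor's effect changes over time.
- That the analysis is invalid. A conservative test does not inflate false positives, and the omission does not bias the group difference.
- That the planned group test starts from about 80% power. A one-way F test on a single outcome gives 0.80 at 0.35 SD (λ = 90 × 4 × 0.175² = 11.0), but the planned group effect, averaged over three waves, gives 0.61 at ICC 0.5 and 0.52 at ICC 0.7.

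**Conclusion.** The point holds for the between-subject group effect. The allocation uses minimisation with HRV in the scoring, and the A1 model omits those factors. The direction follows from the design: a conservative test and lost power wherever the factors are prognostic. Under the working assumptions with ICC 0.5, including them adds about 4, 8, 17 and 27 percentage points of power at R2 of 0.05, 0.10, 0.20 and 0.30 (0.608 to 0.645, 0.687, 0.778 and 0.877). At R2 of 0 the figure stays at 0.608. The gains are somewhat smaller at ICC 0.7. The documents cannot say where in this range the trial lies. The change is a near-free improvement to a primary analysis, and not the repair of an invalid one.

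**What to change.** In the Data Analysis Plan, list every factor used in Qminim, with its categories and weights. Include all of them as covariates in each A1 model, with T1 HRV as a continuous variable. Add factor by time terms for the group by time test. Report the model without covariates as a secondary result.

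The cost is a sentence or two of text and a few degrees of freedom: three binary factors would take the between-subject error from 356 to 353. No new data should be needed, since factor values must exist before a caregiver can be allocated, and the remote-visit gaps in HRV concern T2 and T3 only. Fixing the list before analysis also closes off a later choice of covariates.
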